9.2.3 Subject Populations

The Safety Population will be defined as all subjects who undergo Study Treatment, and the safety analysis will be performed on this population.

The primary analysis on the primary endpoint will be performed on the Intent to Treat (ITT) population, defined as all patients who were treated in the study. All Primary and Secondary endpoints will be analyzed using the ITT population.

A secondary analysis will be conducted on the Per Protocol (PP) population. Since the primary endpoint is at 6 Months, this is all subjects who complete the 6 Month assessment and who do not have a major deviation from the protocol. For all other assessments, this is defined as the subjects who complete those assessments according to the protocol.

10. DATA MANAGEMENT CONSIDERATIONS

10.1Data Collection

The CRFs will be completed based on source documents. Once CRFs have been completed by the site, the data management group will begin the data cleaning process.

10.2Data Management

Once the CRFs are ready for review, the data management group will complete manual validation checks to ensure the quality, consistency, and completeness of all data entered. Instances of incomplete, uninterpretable or inconsistent data will be resolved with the site through issuing a query or other means of communication as necessary. The site is responsible to respond and / or correct the data for all queries issued in a timely manner. All queries and changes to the data will be tracked.

10.3Data Retention

All correspondence related to this clinical study should be archived in appropriate study files. Patient records including consent forms, source documents, CRFs, device records including regulatory authority (CA and IRB/EC) and Sponsor correspondence pertaining to the study must be kept on file. All original subject and device inventory records relating to the study shall be retained for not less than two years following notification by Anika Therapeutics, Inc. that the applicable regulatory authority approved an application for the marketing of the study device or that all investigations using the study device have been discontinued. Thereafter, records will not be destroyed without giving Anika Therapeutics, Inc. prior written notice.

11. CLINICAL SUPPLIES

11.1 Packaging and Labeling

The Sponsor will provide the investigational sites with the investigational product.

Cingal syringes will be labeled with investigational use only labels specific to this clinical trial.

The contents of the syringe are sterile if the syringe is intact. Each Cingal syringe is provided packaged in a sealed container within a carton and should not be used if the container has been opened or damaged.

The syringe, container and carton will have the required labeling information and caution statements.

The investigational sites are responsible for providing the paracetamol rescue medication to subjects.

11.2Storage Requirements

The storage requirements for Cingal are to be maintained in a secure controlled environment at room temperature below 77° F / 25° C. DO NOT FREEZE. Refrigerated Cingal should be allowed to reach room temperature (approximately 20 to 45 minutes) prior to use.

11.3 Instructions for Use

Instructions for Use will be provided within the Investigational Product.

11.4 Device Accountability

It is important to account for the disposition of all Investigational Product (IP) received by a clinical site. Required information includes the date received, date injected, lot number, expiry date and the Subject who received the device.

The site will use a form to document device accountability which will be reviewed by the study monitor during routine monitoring visits. Each time an investigational product is dispensed, the following information should be recorded: Subject ID, date used, Lot Number and the initials of the person completing the device accountability log. At the termination of the study, Anika Therapeutics, Inc. will instruct sites on the disposition of unused investigational product.

12. DATA QUALITY ASSURANCE

Anika Therapeutics, Inc. performs quality assurance checks on all clinical trials that it Sponsors. Before enrollment of a subject in this study, a monitor (from Anika or designee) and the site staff will review the protocol, the CRFs and instructions for completing them, the procedure for obtaining informed consent, the procedure for reporting AEs and all other relevant study procedures and forms.

13. REGULATORY OBLIGATIONS

The Principal Investigator agrees that the clinical study will be conducted according to the relevant national guidelines which may include: International Conference on Harmonization (ICH) E6 Guideline for Good Clinical Practice (GCP), EN ISO 14155:2011, Council Directive 93/42/EEC and Commission Directive 2005/28/EC.

The Principal Investigator agrees that the clinical study will be conducted according to ethical principles that have their origins in the World Medical Association Declaration of Helsinki, and local ethical and legal requirements.

13.1 Clinical Trial Information

Before the beginning of this expanded indication study, the Investigator will be given the Investigator's Brochure. If the Investigator's Brochure is revised during the study, the Investigator will receive a copy of the revised version. The Investigator's Brochure is a confidential communication from Anika Therapeutics, Inc.

Acceptance to participate in this study constitutes an agreement by the recipient investigator that no unpublished information therein contained will be published or disclosed without Anika Therapeutics Inc.'s prior written approval except that these documents must be submitted in accordance with the standard operating procedures (SOPs) of the IRB/EC and other applicable oversight committees with the agreement that these committees are required to keep the information confidential. Institutional Review Board (IRB)/Ethics Committee (EC) Approval

The protocol and the ICF must have the approval of a properly constituted IRB/EC responsible for approving clinical trials at the site. Prior to activation of the site for enrollment, written IRB/EC

Anika Therapeutics, Inc. Cingal 20-03

approval of the protocol and ICF and a signed contract between the site and Sponsor will be obtained.

13.2 Protocol Adherence

The Investigator agrees to conduct the study according to the protocol and agrees that all persons delegated to perform study procedures will do so as well. The Investigator must read the protocol thoroughly and must follow the instructions exactly. Investigators shall propose to Anika Therapeutics, Inc. any appropriate modifications to the Protocol. Any change should be agreed to by Anika Therapeutics, Inc. and the Investigator and documented with written protocol amendments. The Investigator is not to conduct any protocol modifications without prior written permission from Anika Therapeutics Inc. Each Investigator will be responsible for enrolling only those subjects who have met protocol eligibility criteria.

13.3 Amendments to the Protocol

Changes to the study protocol after IRB/EC approval must be documented in a protocol amendment and signed by the Investigator and Sponsor. All amendments must be submitted to the CA and IRB/EC in accordance with applicable regulations. The protocol amendment may be implemented after it has been approved by the appropriate regulatory agencies, unless immediate implementation of the change is necessary for subject safety.

13.4 Protocol Deviations

Deviations from the protocol include, but are not limited to missed assessments, out of window assessments, etc. All protocol deviations will be documented and explained. All subjects with protocol deviations will continue to be followed for improvement and safety. Analysis of study data will be done on both the ITT and PP populations.

13.5 Informed Consent

Written informed consent for each subject participating in the trial will be obtained in accordance with GCP and the relevant national and local regulatory authority requirements. An ICF template will be provided to each Investigator. If changes are made to the template, the Investigator must send a copy of the ICF to Anika Therapeutics Inc. or designee for review to assure compliance with the ICH requirements prior to submitting to the IRB/EC. The IRB/EC approved consent form will be provided to the subject and will be signed prior to any study procedures being performed. One copy of the signed ICF document must be given to each subject in his/her native language and one signed copy must be retained in the subject's file. Subjects will be made aware of any new information that becomes available during the course of the study.

13.6 Adverse Event Reporting

The Investigator agrees to document and report all AEs to Anika Therapeutics, Inc. or its designee. The Investigator is further responsible for ensuring that any study staff promptly brings AEs to the attention of the Investigator. The Investigator is also responsible for informing the participating IRB/EC and other regulatory authorities (as applicable) of any reportable events and adhering to local IRB/EC requirements. The Investigator agrees to supply Anika Therapeutics Inc., upon request, any additional information related to the safety reporting of a particular event. The Investigator shall inform the subject of the nature and possible cause of any AEs experienced.

13.7 Permission to Review Subject's Source Records

The Investigator agrees that Anika Therapeutics, Inc., its employees or agents, and the respective Competent Authorities and Ethics Committees will have the right, both during and after this trial, to audit and review pertinent medical records related to the clinical study. Subject study data will not be identified by name, and confidentiality of information in medical records will be preserved.

13.8 Change in Investigator

If any Investigator retires, relocates, or withdraws from an investigation, the responsibility for conducting the study and maintaining records may be transferred to another person who will accept the responsibility at the same institution. Anika Therapeutics, Inc. must be notified of and agree to the change.

13.9 Study Monitoring

A study monitor from Anika Therapeutics, Inc. or designee will maintain contact with the Investigator and may visit the Clinical Trial Site for the purpose of overseeing the progress of the study, and ensuring it is conducted, recorded and reported in accordance with the protocol, SOPs, GCP and applicable regulatory requirements.

13.10 Confidentiality

All information that is provided to the Investigator regarding Cingal is regarded as confidential. Subjects will be told that data will be handled in compliance with European Union Data Protection Directive or relevant national laws on the protection of personal data. Subjects will be informed that Anika Therapeutics, Inc. or designee will have access to their medical records. Subject's participation in the study will be treated as confidential and subjects will not be referred to by name in any report of the study. The identity of the subjects will not be disclosed in any study records and subjects' data will be described with a unique subject identifier. Subject data will be processed electronically to determine the outcome of this study, and to provide to regulatory authorities.

13.11 Early Study Discontinuation

If the Sponsor, Investigator, or Medical Monitor discover conditions during the study that indicate that the study or a Clinical Trial Site should be terminated, this action may be taken after appropriate consultation between the Sponsor, Investigator, and Medical Monitor as applicable.

Conditions that may warrant termination include, but are not limited to:

- The discovery of any unexpected, serious, or unacceptable risk to subjects enrolled in the study,
- The decision on the part of the Sponsor to suspend or discontinue testing, evaluation, or development of the device.
- Failure of the Investigator to comply with GCP guidelines,
- Submission of knowingly false information from the research facility to the Sponsor, Clinical Monitor, or regulatory authorities,
- Insufficient adherence to protocol requirements.

If Anika Therapeutics, Inc. and/or the Investigator should discover conditions arising during the study that indicate it should be terminated, an appropriate schedule for termination will be instituted. Anika Therapeutics, Inc. also reserves the right to discontinue this study for administrative reasons at any time.

If a trial is suspended, Anika Therapeutics Inc. will promptly inform the Investigators/institutions, and the regulatory authority(ies) of the termination or suspension and the reason(s) for the termination or suspension. The Investigator should notify the IRB/EC promptly and provide the reason(s) for the termination or suspension by the Sponsor or by the Investigator/institution.

13.12 Subject Withdrawal

Each subject is free to discontinue from the study at any time, for any reason. If a subject discontinues the study, the Investigator will record the reason for withdrawal on the CRF. Examples of reasons for premature withdrawal of a subject from the study include:

- Current illness that would, in the judgment of the Investigator, affect study assessment to a significant degree
- Subject noncompliance with follow-up assessments
- · Subject request to withdraw
- Subject lost to follow-up
- Termination of the site's study participation by Anika Therapeutics, Inc., the institution or IRB/EC
- Other (reason to be documented in the CRF)

Every effort shall be made to have withdrawn subjects return for the required safety evaluations as detailed in the protocol.

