6. ENDPOINTS

6.1 Primary Endpoint:

 Reduction of index ankle Numerical Rating Scale (NRS) pain on walking from baseline to 6 Months post injection.

6.2 Secondary Endpoints:

- Improvement in AOFAS index ankle from baseline to 6 months post injection.
- Improvement in Patient Global Assessment (PGA) from baseline to 6 months post injection.
- OMERACT-OARSI in the index ankle responder rate at 6 months post injection.
- Time to treatment failure
- Reduction in Medication usage from baseline to 6 months post injection.

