7.4 Baseline Visit: Treatment Visit (Day 0)

The Baseline Visit (Day 0) will occur 7 to 14 days after the Screening Visit to allow for rescue medication washout. The injection will occur at this Baseline visit along with the following activities:

Before Treatment Injection

- Concomitant Medications
- Current non-drug therapies
- Confirm Medication Washout
 - If subject did not complete medications washout, reschedule the visit to allow washout to be completed.
- Patient Global Assessment (PGA)
- AOFAS index
- Index & Contralateral Hip, Knee and Ankle Joint Pain on Walking (NRS Scale)
 - o Confirm the Baseline Inclusion & Exclusion criteria for NRS Pain on Walking
- Physical Exam of Index and Contralateral Hip, Knee and Ankle Joints

Treatment Procedure

The Treating Physician may perform the Study Injection to the index ankle as standard of care dictates or delegate the injection to qualified study staff.

Intra-articular injection of the index ankle joint may be conducted under fluoroscopic or ultrasound guidance as required by standard of care treatment. Guidelines for the injection procedural steps are provided below. Modifications to this technique should be recorded in the CRFs.

- Patient is supine.
- Prep the skin at injection site with 1% betadine solution or equivalent.
- Peri- articular injection site anesthesia of lidocaine or topical refrigerant anesthetic (e.g. ethyl chloride) may be utilized.
- The ankle is dorsiflexed to a neutral position. Injection site is located in the anteromedial portal of the ankle joint as described for ankle arthroscopy
- Fluoroscopic or ultrasound guidance may be utilized if required to insert 18-21 gauge needle. Traction can be applied if required to gain access.
- Insert needle until resistance against the articular surface and then withdraw the needle 1-2 mm.
- If using fluoroscopic guidance, a small amount of fluoroscopic contrast agent (0.5 to 1.0 ml) should be injected through the needle to verify intra-articular placement.
- If using ultrasound guidance, a small volume of air (up to 0.5 ml) may be injected to verify IA

positioning.

- If pooling of the contrast agent or air around the needle tip is observed, the needle should be repositioned.
- When contrast agent or air is successfully injected into the joint, intra-articular placement is confirmed.
- Following confirmation of intra-articular needle placement, the joint may be aspirated to remove synovial fluid.

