8.2 Safety Reporting Process – principal investigator responsibilities

The principal investigator shall report all adverse events and device deficiencies in the appropriate sections of the e-CRF and provide where requested by the sponsor, the necessary clinical or technical information that may contribute to clarifying the circumstances.

The principal investigator shall report all serious adverse events (SAEs) and device deficiencies (DDs) that might have led to a SAE: if a) suitable action had not been taken or b) intervention had not been made or c) if circumstances had been less fortunate, to the sponsor within 24 hours after knowledge of the event using the appropriate e-CRF.

When required by national or local regulations, the principal investigator shall also notify the EC/IRB and Regulatory Agencies of all reportable events according to national regulations within the by regulations required timelines and may also be requested by the EC/IRBs to provide annual reports. The principal investigator shall document all adverse events and device deficiencies in the e-CRF from the point of enrollment until the subject is exited from the study.

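### Section 13.12 permits withdrawal of injected subjects for missed assessments or illness and then seeks only safety data, so the Month 6 pain score can be selectively missing

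*Protocol*

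**What the plan says.** Protocol 7.4 places the sole study treatment on Day 0: "The injection will occur at this Baseline visit along with the following activities". The primary endpoint (Protocol 6.1) is "Reduction of index ankle Numerical Rating Scale (NRS) pain on walking from baseline to 6 Months post injection". Protocol 9.2.3 and SAP 4.5 analyse it in the ITT population, defined as everyone treated.

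Protocol 13.12 has the investigator record why a subject left and gives examples of reasons for premature withdrawal. Two matter here: "Subject noncompliance with follow-up assessments" and "Current illness that would, in the judgment of the Investigator, affect study assessment to a significant degree". A subject's own request and loss to follow-up are separate entries. The section closes: "Every effort shall be made to have withdrawn subjects return for the required safety evaluations as detailed in the protocol". It does not mention the pain score, the PGA or the AOFAS, and the schedule in 7.1 has no withdrawal visit.

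Protocol 13.4 takes a different line on missed visits: "Deviations from the protocol include, but are not limited to missed assessments, out of window assessments, etc", and "All subjects with protocol deviations will continue to be followed for improvement and safety".

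On adverse events, 8.2 tells the investigator to "document all adverse events and device deficiencies in the e-CRF from the point of enrollment until the subject is exited from the study", whereas 6.4 runs collection to the 6-month assessment. Protocol 7.5 requires at least three documented attempts to contact a subject about scheduled follow-up.

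**The concern.** After the injection there is no further study treatment to stop, so taking a subject out of the study ends data collection only. For two of the listed reasons the site has some say in whether that happens, and once it has, the protocol does not ask for the outcome on which the trial is judged.

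A subject who misses Month 1 should stay in efficacy follow-up under 13.4 but may be withdrawn under 13.12. Two sites could handle the same subject differently and both be following the protocol.

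The primary analysis is a one-sample t-test on change from baseline with no control arm, so nothing offsets a selective loss. Neither Protocol section 9 nor the SAP says what happens to a missing Month 6 score, and PROC UNIVARIATE (SAP 4.1.2.1) would use observed changes only. The analysis of all treated subjects would in practice become an analysis of those with a score. Subjects who miss visits or fall ill are unlikely to be a random subset. If they do worse, the reported mean reduction is too favourable, and scores that were never requested cannot be recovered later.

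**Working it through.** **Step 1: the passages side by side.**

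| Situation after injection | Protocol 13.4 | Protocol 13.12 |
|---|---|---|
| Missed assessments | Deviation; follow-up continues for improvement and safety | May be withdrawn; recalled for safety only |
| Illness judged to affect assessment | Not named as a deviation | May be withdrawn; recalled for safety only |

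The first row is a conflict. The second is not; there the issue is only that an outcome which could be measured is not requested.

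**Step 2: reproduce the plan's sample size.** Inputs from Protocol 9.1: mean change 2, SD 2 to 2.5, power 80%, alpha 5%, 15 required, 25 to be treated. For a one-sample t-test with exact noncentral-t power, the smallest n reaching 80% is:

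- SD 2.5: 15 two-sided (power 82.1%), 12 one-sided
- SD 2.0: 10 two-sided, 8 one-sided

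The stated 15 reproduces at SD 2.5 with a two-sided test.

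**Step 3: is power at risk?** The margin between 25 and 15 is 10 subjects, 10/25 = 40%. This is subtraction; the plan states no dropout rate. At a mean of 2, SD 2.5, two-sided 5%:

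- 25 observed: 97.0%
- 20 observed: 92.4%
- 15 observed: 82.1%

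So power is adequate even if all ten are lost.

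**Step 4: the possible bias.** Let m of 25 be missing, completers average c, and the missing average w. Then

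all-treated mean = [(25 − m)·c + m·w] / 25, and the completers' mean overstates it by (m/25)·(c − w).

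Assume c = 2.0. The values of m and w are also assumptions; the documents give neither.

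| m | w = 0 | w = 1 |
|---|---|---|
| 2 | (23×2.0 + 0)/25 = 1.84 | (46 + 2)/25 = 1.92 |
| 5 | (20×2.0 + 0)/25 = 1.60 | (40 + 5)/25 = 1.80 |
| 10 | (15×2.0 + 0)/25 = 1.20 | (30 + 10)/25 = 1.60 |

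Each is below the 2 points that Protocol 9.1 treats as clinically significant, while the completers' mean would read 2.0. If the missing did better than completers, the sign reverses.

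**Step 5: would the test against zero change?** Take the most extreme cell, an observed all-treated mean of 1.2 with n = 25.

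- SD 2.5: t = 1.2/(2.5/√25) = 2.40.
- Adding the spread between the two groups: SD = √(2.5² + 0.4×0.6×2²) = √7.21 = 2.685, so t = 1.2/(2.685/5) = 2.23.

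Both exceed the two-sided 5% critical value of 2.06. What is exposed is the size of the reported reduction more than the rejection of zero.

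**The case against.** The strongest reply is that 13.12 is mainly a list for coding reasons. It offers examples, sets no threshold and instructs nobody to withdraw a subject. That is correct. A reader might infer that the protocol requires these withdrawals, or makes the loss of scores inevitable; the text supports only that it permits them without asking for the endpoint afterwards.

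Second, 13.4 and 13.12 can be read in sequence: one missed visit is a deviation, while persistent non-attendance becomes a reason for withdrawal. That reading is reasonable, but neither section states it, and 13.4 speaks of all subjects with deviations. Sites are left to choose.

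Third, the protocol has safeguards. The contact attempts in 7.5 will reduce losses. There is no separate safety visit, so a recalled subject would probably attend a visit at which the pain score is a listed procedure (7.1, 7.6). Collecting it is therefore not forbidden. But 7.5 serves the follow-up schedule, and nothing extends efficacy collection to someone already withdrawn. Protocol 13.15 also requires the consent material to explain follow-up after withdrawal. Those pages are not in the copy reviewed, so what subjects are told is unknown.

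Fourth, 8.2 conflicts with the safety recall only if a withdrawn subject counts as exited, a term the protocol does not define. For completers, 8.2 and 6.4 agree. This is an ambiguity to close, not a flat contradiction.

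Fifth, the illustration attributes every loss to the two disputed reasons, although subject request, loss to follow-up and site closure would also contribute and would remain. This stands, and it means the avoidable part may be smaller than the table shows.

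Finally, scores obtained by phone may lack the 48-hour rescue washout in 7.3.9.2. This also stands, and the fix has to allow for it.

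**Conclusion.** The point holds in a limited form. Followed as written, 13.12 lets a site end efficacy follow-up of a treated subject for missed assessments or illness, and afterwards only safety data are sought. The conflict with 13.4 covers missed assessments alone; a reader might extend it to illness, but 13.4 does not name illness as a deviation.

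The consequence is possible bias in the mean reduction. With completers averaging 2.0 and 5 of 25 missing, the overstatement would be 0.4 points if the missing did not change and 0.2 if they improved by 1 point. These rest on assumed losses and outcomes, and the true size is unknown. It would be wrong to infer that the trial is underpowered, that the plan expects 40% loss, or that the primary test would fail: Steps 3 and 5 do not support any of these. This is an inexpensive improvement to conduct, not a flaw that invalidates the design.

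**What to change.** 1. Reconcile 13.12 with 13.4, stating that missed assessments or intercurrent illness alone do not end follow-up of an injected subject.
2. Extend the last sentence of 13.12. Withdrawn subjects who still agree to contact are asked for the Month 6 index-ankle pain score, adverse events and any new ankle treatment at the same contact as the safety evaluation, by phone if needed.
3. Record how each such score was collected and whether the 48-hour rescue washout was met, so that these scores can be flagged in a sensitivity analysis.
4. Align 8.2 with 6.4 so that adverse events in these subjects are recorded to the 6-month assessment.

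The cost is protocol wording plus a short CRF page or phone script for a few subjects. The drawback is that a few scores will come by phone or without washout, which item 3 makes visible. Subjects who refuse further contact will still be missing.
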